#### 5.6.4.5. *ACEND*

Parents/caregivers of participants will complete the ACEND questionnaire. The ACEND questionnaire will not be collected for adult participants who do not require a caregiver during the study visits. For cohort 1, only the parents/caregivers of the participants older than 2 years will complete this questionnaire. This assessment instrument has been designed to quantify the caregiver impact experienced by parents/caregivers of children affected with severe neuromuscular diseases, including children with SMA [Matsumoto 2011]. ACEND includes seven domains assessing physical impact (including feeding/grooming/dressing, sitting/play, transfers, and mobility) and general caregiver impact (including time, emotion, and finance). and each domain comprises several items.

The total score for a domain with n items, each item assessed on ordinal scale from 1 to z, is derived as follows: 100 multiplied by (Mean of the n items in the domain -1) divided by (z-1).

This total score will be on a scale of 0 to 100 with a higher score indicating a greater impact on the caregiver.

At least two items for the time domain and one item for the remaining domains need to be nonmissing for a total to be calculated; else the total score will be set to be missing.

#### Analyses

- Total score and change from baseline by visit
- Domain total score and change from baseline by visit
- Mean (-/+ SE) plots of total score and change from baseline.

#### **5.6.4.6. CHOP INTEND**

The CHOP INTEND test was specifically designed to evaluate the motor skills of infants with significant motor weakness, including infants with SMA [Glanzman 2010]. The CHOP INTEND test captures neck, trunk, and proximal and distal limb strength in 14 elicited and 2 observational items. The CHOP INTEND has been established as a safe and reliable infant motor measure in infantile-onset SMA and has been validated [Glanzman 2011].

The CHOP INTEND infant motor function scale is comprised of 16 test items, nine of which are scored 0, 1, 2, 3, or 4 with greater scores indicating greater muscle strength, five are scored as 0, 2, or 4, one is scored as 0, 1, 2, or 4, and one as 0, 2, 3, or 4. This can result in a worst possible total score of 0 to a best possible total score of 64. CHOP INTEND is used to assess spontaneous movement in the upper extremities, spontaneous movement in the lower extremities, hand grip, head in midline with visual stimulation, hip adductors, rolling elicited from the legs, rolling

Product: Nusinersen	Statistical Analysis Plan
Study: 232SM203	Version: 1.0 Final

elicited from the arms, shoulder and elbow flexion and horizontal abduction, shoulder flexion and elbow flexion, knee extension, hip flexion and foot dorsiflexion, head control, elbow flexion, neck flexion, head/neck extension, and spinal incurvation. CHOP INTEND is to be evaluated during the study for cohort 1. For each item, a score will be collected on the left and right side.

In order to examine if the response is consistent with a range of thresholds, the proportion of participants achieving: worsening of  $\geq=6$ ,  $\geq=5$ ,  $\geq=4$ ,  $\geq=3$ ,  $\geq=2$ ,  $\geq=1$  points, no change (=0 points), and improvement of  $\geq=1$ ,  $\geq=2$ ,  $\geq=3$ ,  $\geq=4$  (endpoint for main analysis),  $\geq=5$ ,  $\geq=6$  points will be presented. If a subject has moved scales and/or reached maximum score of 64 will be summarized on a different row in the tables.

Depending on data availability the following displays will be presented showing the following

- Total score and change from baseline by visit
- Thresholds of change from baseline by visit

#### 5.6.4.7. HINE Section 2

Hammersmith Infant Neurological Examination (HINE) is collected for cohort 1 infantile-onset SMA subjects, that are less than 2 years of age at the time of informed consent.

The assessment is comprised of eight motor milestone categories: voluntary grasp, ability to kick in supine position, head control, rolling, sitting, crawling, standing and walking.

Within each motor milestone category (depicted as Motor Milestones in Table 5), there are 3 to 5 levels that can be achieved (depicted as Milestones Progression, or rows, in the Table above). All 8 Motor Milestones are tested during each assessment. A subject whose results after testing all appear in the first column (No grasp, No kicking, Unable to maintain head upright, etc.) has not achieved any motor milestone. Motor milestone achievement is depicted by movement from the left side of the Table above to right side of the Table, as denoted by the Milestone Progression arrow in the Table.

The 8 categories of HINE Section 2 can be summed to give a total score that ranges from 0 to 26.

Depending on data availability the following displays:

- Total motor milestone score and change from baseline by visit
- Summary of highest motor milestones item achieved at last observed assessment.
- The proportion of subjects who have achieved specific individual item at last analysis visit.
- Mean (-/+ SE) plots of total score and change from baseline.

#### Table 5:Hammersmith Infant Neurological Examination Section 2 - Motor Milestones

Motor Milestone Category					
	0	1	2	3	4
Voluntary grasp	No grasp	Uses whole hand	Finger and thumb/ immature grasp	Pincer grasp	
Ability to kick (in supine)	No kicking	Kicks horizontal; legs do not lift	Upward (vertically) [3 months]	Touches leg (4 to 5 months)	Touches toes (5 to 6 months)
Head control	Unable to maintain upright (< 3 months)	Wobbles (4 months)	All the time upright (5 months)		
Rolling	No rolling	Rolls to side (4 months)	Prone to supine (6 months)	Supine to prone (7 months)	
Sitting	Cannot sit	Sits with support at the hips (4 months)	Props (6 months)	Stable sit (7 months)	Pivots (rotates) [10 months]
Crawling	Does not lift head	On elbow (3 months)	On outstretched hand (4 to 5 months)	Crawls flat on the abdomen (8 months)	On hands and knees (10 months)
Standing	Does not support weight	Supports weight (4 to 5 months)	Stands with support (8 months)	Stands unaided (12 months)	

Motor Milestone Category	Milestone Level Progression Score (Age Expected in Heathy Infants  ) Improvement				
	0	1	2	3	4
Walking	No walking	Bouncing (6 months)	Cruising (holding on) [11 months]	Walks independently (15 months)	

Values for healthy infants in [De Sanctis 2016; Haataja 1999]

#### 5.6.4.8. Number and Length of Hospitalizations

The number of hospitalizations during the study will be analyzed using the rate at which they occur. For descriptive purposes, the aggregate hospitalization rate will be calculated for each group by dividing the total number of hospitalizations that occurred in the group by the total number of subject-years on study.

Annualized hospitalization rate will be calculated for each subject as the number of hospitalizations that the subject experienced divided by the number of days on study and this ratio multiplied by 365.

For each subject, the total time spent in hospital during the study will be calculated and prorated according to number of days on study.

# 5.6.4.9. CGIC

The CGIC rating scale was developed as a brief standalone assessment of the clinician's view of the patient's global functioning after initiating a study medication [Guy 1976]. The CGIC provides an overall clinician-determined summary measure that takes into account all available information, including knowledge of the patient's history, psychosocial circumstances, symptoms, behavior, and the impact of the symptoms on the patient's ability to function. The CGIC is administered by an experienced clinician makes a judgment about the total picture of the patient at each visit: the severity of the illness, the patient's level of distress and other aspects of impairment, and the impact of the illness on functioning. The CGIC is rated without regard to the clinician's belief that any clinical changes are or are not due to medication and without consideration of the etiology of the symptoms.

The CGIC is a 7-point scale that requires the clinician to assess how much the patient's illness has changed relative to a baseline state at the beginning of the intervention and is rated as follows: 1, very much improved; 2, much improved; 3, minimally improved; 4, no change; 5,

Product: Nusinersen	Statistical Analysis Plan
Study: 232SM203	Version: 1.0 Final

minimally worse; 6, much worse; or 7, very much worse. CGIC should be assessed consistently by the same rater for each study participant. A separate CGIC assessment will be performed by the Investigator (Principal Investigator or Sub investigator) and caregiver.

In order to investigate response on these scales, three definitions of responder will be defined: "Much improved": Responder (<=2) versus Non-responder (>=3), "Any improvement": Responder (<=3) versus Non-responder (>=4), "No worsening": Responder (<=4) versus Nonresponder (>=5).

Analyses

• Proportion of participants achieving each responder definitions above by visit

#### 5.6.4.10. Number of Serious Respiratory Events

All adverse events that are coded into the System Organ Class (SOC) of respiratory, thoracic, and mediastinal disorders, either as their primary SOC or their secondary SOC will be considered respiratory events. Only those classified as serious will be analyzed. By utilizing the above approach, rare occurrence of serious respiratory events in the Infection and Infestation SOC and Investigation SOC (if any) may not be included. However, a detailed review of the AE listing will be conducted to identify such events.

The number of serious respiratory events during the study will be analyzed using the rate at which they occur. For descriptive purposes, the aggregate rate will be calculated for each group by dividing the total number of serious respiratory events that occurred in the group by the total number of subject-years on study.

In order to evaluate if there is any change in the number of serious respiratory events overtime, the events will be presented in periods of 120 days.

#### 5.6.4.11. Ventilator Use

The participant's use of ventilators and respiratory aids will be collected at every study visit.

[figure not shown]
The ventilation/respiratory aid use will be summarized by visit and listed.

[figure not shown]

Product: Nusinersen	Statistical Analysis Pla
Study: 232SM203	Version: 1.0 Fin
•	
•	
•	
•	

Product: Nusinersen	Statistical Analysis Plan
Study: 232SM203	Version: 1.0 Final
	-
•	
•	
•	
•	

Product: Nusinersen	Statistical Analysis Plan
Study: 232SM203	Version: 1.0 Final
•	
• • •	
•	

#### **Safety Endpoints** 5.7.

Analyses of safety data will include adverse events and serious adverse events, laboratory data, ECGs, growth parameters, vital signs, and neurological examinations. Worsening or new

Product: Nusinersen	Statistical Analysis Plan
Study: 232SM203	Version: 1.0 Final

findings noted from the physical or neurological examinations will be reported as AEs as appropriate.

# 5.7.1. Adverse events

All adverse events (AEs) will be analyzed based on the principle of treatment emergence. An adverse event will be regarded as treatment-emergent if it was present prior to receiving the first dose of nusinersen in 232SM203 and subsequently worsened in severity or was not present prior to receiving the first dose of nusinersen and subsequently appeared. Refer to Appendix A for more details about AE with missing start or stop dates.

The incidence and frequency (event count) of treatment-emergent adverse events will be summarized. A participant having the same adverse event more than once will be counted only once in the incidence for that adverse event; multiple occurrences of the same adverse event for the same subject will all be counted in the frequency for that adverse event. Incidence will be presented by decreasing order by system organ class and by decreasing order by preferred term within each system organ class.

The occurrence of the AE with the greatest severity will be used in the calculation of incidence by severity. The AE relationship to treatment or LP procedure is captured as related or not related. In the event the relationship is missing then this will be considered related.

Due to the long half-life of nusinersen, analyses of adverse events will include all events reported during the study per the treatment emergent definition. Adverse Events will be coded using the Medical Dictionary for Regulatory Activities.

The following presentations will be shown:

- an overall summary showing, the number and percentage of subjects with an adverse event, a mild, moderate or severe event, an event related to study drug, an event related to lumbar puncture procedure, a serious event, a serious event related to study drug, an event leading to study drug withdrawal, an event leading to study withdrawal, and a fatal event.
- incidence and frequency by system organ class and preferred term
- incidence and frequency by preferred term
- incidence and frequency, by preferred term, at least 5% of subjects in either study group
- incidence of adverse events by maximum severity by preferred term
- incidence and frequency of severe events by system organ class and preferred term
- incidence and frequency of events related to study drug by system organ class and preferred term
- incidence and frequency of events related to lumbar puncture (as assessed by the investigator) by system organ class and preferred term

Product: Nusinersen	Statistical Analysis Plan
Study: 232SM203	Version: 1.0 Final

- incidence by system organ class and preferred term that occurred within 24 hours of dosing procedure
- incidence by system organ class and preferred term that occurred within 72 hours of dosing procedure
- incidence and frequency of serious adverse events by system organ class and preferred term
- incidence and frequency of serious adverse events related to study drug by system organ class and preferred term
- incidence of events that led to fatal outcome
- incidence of events leading to study drug withdrawal by system organ class and preferred term
- incidence and frequency of adverse events over time by system organ class and preferred term.
- incidence of events leading to withdrawal from study by system organ class and preferred term
- incidence and frequency of adverse events antibody status by system organ class and preferred term.

A separate table will also be presented to show an overall summary of COVID-19 pandemic related AEs.

Listings of the following events will be produced.

- AEs
- SAEs
- AE with fatal outcome
- AEs led to study drug withdrawal
- AEs led to withdrawal from study
- AEs related to lumbar puncture procedure
- AEs related to study drug

# 5.7.2. Clinical laboratory data

Laboratory data will be evaluated to determine the incidence of abnormalities that emerge during the course of the study. Changes in laboratory evaluations will be presented relative to baseline, which is defined as the closest non-missing visit prior to the first dose.

\_\_\_\_\_

Product: Nusinersen	Statistical Analysis Plan
Study: 232SM203	Version: 1.0 Final

The following clinical laboratory parameters are to be assessed:

- Hematology panel: complete blood count with differential and platelet count (hematocrit, hemoglobin, platelets, red blood cell count [RBC], white blood cell count [WBC], basophils, eosinophils, lymphocytes, monocytes, neutrophils)
- Blood chemistry panel: albumin, total bilirubin, direct and indirect bilirubin, alkaline phosphatase, alanine aminotransferase (ALT) (SGPT), aspartate aminotransferase (AST) (SGOT), gamma-glutamyl transferase (GGT), sodium, potassium, calcium, chloride, phosphate, blood urea nitrogen (BUN), creatinine, cystatin, creatine phosphokinase, creatine kinase, bicarbonate (CO2), glucose, total protein.
- Urinalysis: specific gravity, pH, protein, glucose, ketones, bilirubin, blood, red blood cells, white blood cells, epithelial cells, bacteria, casts and crystals
- Urine total protein assessed by local laboratories
- CSF analysis: RBC, WBC, protein, glucose.
- Coagulation: PT (prothrombin time), aPTT (activated partial thromboplastin time), and INR (international normalized ratio).

Each hematology, blood chemistry, coagulation and CSF laboratory parameter will be flagged as "low", "normal" or "high" relative to the parameter's normal range or as "unknown" if no result is available.

For each urinalysis laboratory parameter, the number and percentage of subjects experiencing postdose shifts to abnormal will be summarized.

For each hematology, blood chemistry, coagulation and CSF parameter, the number and percentage of subjects experiencing postdose shifts to 'low' or 'high' will be summarized. In each summary, the denominator for the percentage is the number of subjects at risk for the shift. The number at risk for the shift to low is the number of subjects whose baseline value was not low and who had at least one post baseline value. The number at risk for the shift to high is the number of subjects whose baseline value was not low and who had at least one post baseline value. The number at risk for the shift to high is the number of subjects whose baseline value was not low and who had at least one post baseline value. The number at risk for the shift to high is the number of subjects whose baseline value was not high and who had at least one-post baseline value. Subjects will be counted only once for each parameter and each shift regardless of how many postdosing assessments had that type of shift. All post baseline data will be used in the shift tables, regardless of whether a scheduled or unscheduled visit.

Also, for each parameter, the incidence of shift to low will be summarized using the minimum post baseline values. Shift to low includes subjects with a normal, high, or unknown baseline value and at least one post baseline value of the given test. Similarly, the incidence of shift to high will be summarized using the maximum post baseline values. Shift to high includes subjects with a low, normal, or unknown baseline value and at least one post baseline value.

To evaluate potential serious hepatotoxicity subjects with a post baseline AST and/or ALT value  $\geq$ 3 times the upper limit of normal (ULN) and a post baseline bilirubin value >2 times ULN at any time, not necessarily concurrent, will be listed with their values. In addition, a plot will be

Product: Nusinersen	Statistical Analysis Plan
Study: 232SM203	Version: 1.0 Final

presented with each subject's maximum post baseline AST or ALT value relative to the ULN against the subject's maximum post baseline bilirubin value relative to the ULN; values do not have to be concurrent. All post baseline data will be used to identify abnormalities, regardless of whether a scheduled or unscheduled visit.

Summary statistics for actual values and change from baseline in laboratory values will be summarized by study group and visit. Line plots for chemistry, hematology and CSF showing median value for each study group at each visit will also be presented.

For a parameter if the local and central result are available with the same date and time then only the central analysis result will be considered for presentations by visit. In a situation where two or more results have the same date and time and are both central (or both local) then we will check with the Safety physician if it would be more appropriate or take the highest or lowest value.

Listings of all chemistry, hematology, coagulation, CSF, urinalysis values and pregnancy test (serum and urine) will be provided.

For platelets a summary of the proportion of participants with a post baseline platelet count below the lower limit of normal on at least 2 consecutive measurements will be presented.

The urine protein positive (trace, +1, +2, +3, +4 or >0.2g/L) results will be presented, number of subjects with positive result at baseline, with a negative result at baseline and at least one and at least two positive post baseline result respectively.

# 5.7.3. Neurological Examinations

# 5.7.3.1. Hammersmith infant Neurological Examination (Sections 1 and 3) (HINE 1 and 3) in infantile-onset SMA population

Sections 1 (neurological items) and 3 (behavior) of the HINE serve as the basis for neurological examinations for infantile-onset SMA subjects < 2 years old in cohort 1. These are to be assessed at Screening, predose and at 3, 6, and 24 hours postdose on Day 1, predose and 1, 3 hours postdose on Days 121 and 241, and on Day 302/ET

The neurological items comprise cranial nerve function (facial appearance, eye appearance, auditory response, visual response, sucking/swallowing), posture (head in sitting position, trunk in sitting position, arms at rest, hands, legs in sitting position, legs in supine and standing positions, feet in supine and standing positions), movements (quantity, quality), tone (scarf sign, passive shoulder elevation, pronation/supination, adductors, popliteal angle, ankle dorsiflexion, pulled to sit, ventral suspension), and reflexes and reactions (tendon reflexes, arm protection, vertical suspension, lateral tilting, forward parachute). Behavior is comprised of state of consciousness, emotional state, and social orientation.

Since the number of patients below 2 years of age is expected to be small the results of HINE 1 and 3 testing will be listed only.

Product: Nusinersen	Statistical Analysis Plan
Study: 232SM203	Version: 1.0 Final

# 5.7.3.2. Neurological Examination in patients 2 years or older

Neurological examinations include assessment of mental status, level of consciousness, cranial nerves, reflexes, motor system, coordination/cerebellar function and sensation – temperature and vibration. These are to be assessed at Screening, predose and at 3, 6, and 24 hours postdose on Day 1, predose and at 1, 3 hours on Days 121 and 241, and on Day 302/ET.

The results collected for the majority of the tests are classified as 'normal' or 'abnormal', however the assessment of sensations is reported as 'present' or 'absent' and the assessment of reflexes is captured on an ordinal scale. For each test it is recorded if secondary to SMA.

# Acute Effects After Dosing: Reflex assessments

On each dosing day, each predose reflex will be compared with all the post dosing assessments with 24 hours to see if the subject has changed (gained or lost) or maintained, reflexes. For this comparison the predose reflex status will be categorized into two categories: 0 and  $\geq 1$ . For each reflex, visit, predose category the number and proportion of subjects who change or maintained will be presented.

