### Chronic effects: Reflex and other assessments

For each item and subject, the lowest predose post baseline and the highest predose post baseline outcomes will be determined and 'shift' tables showing the shifts from baseline (predose value on Day 1) to the lowest predose post baseline and from baseline to the highest predose post baseline value will be presented. In this analysis, all assessments after the first dose will be considered post baseline visits.

For all the assessments the summary statistics for actual values and change from baseline in each parameter will be presented by treatment group and visit. Line plots for each item mean value for each treatment group at each visit and timepoint will also be presented.

Product: Nusinersen	Statistical Analysis Plan
Study: 232SM203	Version: 3.0 Final

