# 6.1.3. Neurological Examinations

Neurological examinations include assessment of mental status, level of consciousness, cranial nerves, reflexes, motor system, coordination/cerebellar function and sensation – temperature and vibration. These are to be assessed at Screening, predose and at 3, 6, and 24 hours postdose on dosing Days 1, 15, predose and at 1 and 3 hours postdose on Days 29, 64, 135, 183, and 279; and at Day 302/ET.

The results collected for the majority of the tests are classified as 'normal' or 'abnormal', however the assessment of sensations is reported as 'present' or 'absent' and the assessment of reflexes is captured on an ordinal scale. For each test it is recorded if secondary to SMA.

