#### **Chronic effects: Reflex assessments**

For each reflex the baseline reflex will be compared (the predose value on Day 1) to the pre dose value on later dosing days (Day 1, 15, 29, 64, 135,183, 279 and on Day 302/ET) to see if the subject has changed (gained or lost) or maintained, reflexes. For this comparison the predose reflex status will be categorized into two categories: 0 and  $\geq 1$ . For each reflex, visit, predose category the number and proportion of subjects who change or maintained will be presented.

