#### Chronic effects: Other assessments with binary response (Normal/Abnormal)

For each test the shift from baseline to (the predose value on Day 1) the predose value on later dosing days (Day 1, 15, 29, 64, 135, 183, 279 and on Day 302/ET) to determine, the number and proportion of subjects who moved from 'Normal' to 'Abnormal' will be presented, for sensations the number and proportion who move from 'Present' to 'Absent' will be presented.

Figures of subjects neurological exams will also presented.

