# Chronic effects: Other assessments with binary response (normal/abnormal; present/absent)

For each test the shift from baseline to (the predose value on Day 1) to the predose value on later dosing days and to Day 1, 121, 241 and on Day 302/ET will be determined, the number and proportion of subjects who moved from 'normal' to 'abnormal' will be presented, for sensations the number and proportion who move from 'present' to 'absent' will be presented.

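### In Part C and later-onset Part B, graded reflexes are tabulated as 0 versus ≥1 with no rule for postdose grades, and Part C plans no change-from-baseline reflex comparison

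*SAP*

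**What the plan says.** **Part C SAP, 5.7.3.2 (participants aged 2 years or older).** Most neurological tests are binary, but "the assessment of reflexes is captured on an ordinal scale". The acute reflex section compares each predose reflex with the assessments over the following 24 hours. It then says "For this comparison the predose reflex status will be categorized into two categories: 0 and" ≥1, and gives the number and proportion who changed or maintained within each predose category. The only chronic section is headed "Chronic effects: Other assessments with binary response (normal/abnormal; present/absent").

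**Later-onset Part B SAP, 6.1.3.** Here too, the assessment of "reflexes is captured on an ordinal scale". The acute section uses the same two predose categories. A separate chronic reflex section compares Day 1 predose with later predose values and Day 302, "to see if the subject has changed (gained or lost) or maintained, reflexes", again with predose status as 0 or ≥1. The section ends with "Figures of subjects neurological exams will also presented", without saying what the figures contain.

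**Infantile-onset Part B SAP, 7.1.4.** It has the same 0 versus ≥1 acute display and adds shifts for reflexes as well as other items. Acute shifts run from predose to the lowest and highest values after each dose. For chronic effects, "For each item and subject, the lowest predose post baseline and the highest predose post baseline outcomes will be determined", with shift tables from baseline and summary statistics of actual values and change.

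**Endpoint status.** Change from baseline in neurological examination outcomes is a primary endpoint in Part C (2.1) and a secondary safety endpoint in later-onset Part B.

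**The concern.** An ordinal scale is collected so that degrees of change can be seen. Once the grades are split into absent and present, the table can show a reflex disappearing or appearing. It cannot show a present reflex becoming weaker or brisker. That matters in the two parts where neurological examination is a named safety endpoint and the doses are above the approved 12 mg.

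Part C has a second gap that depends on no interpretation. Its reflex analysis is confined to each dosing day. The drift that a change-from-baseline endpoint is meant to capture, from Day 1 predose through Days 121 and 241 to Day 302, has no reflex display.

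**Working it through.** The SAP states no figure on this point, so there is nothing to reproduce. The check compares the texts and then counts transitions.

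**1. Reflex-specific displays in each SAP**

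| SAP | Acute, 0 vs ≥1 | Acute, lowest/highest shift | Chronic, 0 vs ≥1 | Chronic, lowest/highest shift |
|---|---|---|---|---|
| Infantile-onset Part B, 7.1.4 | yes | yes | no | yes |
| Later-onset Part B, 6.1.3 | yes | no | yes | no |
| Part C, 5.7.3.2 | yes | no | no | no |

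The Part C chronic section counts moves from normal to abnormal, and from present to absent for sensations. Neither applies to a reflex grade.

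**2. What the acute rule does with an example.** Take a predose grade of 3 and a postdose grade of 1. The text categorises predose status only.

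- Reading A: the postdose grade is split the same way. Both grades are ≥1, so the reflex is maintained. This is the natural reading of gained or lost.
- Reading B: any difference in grade counts as a change. The reflex is changed, but every predose grade ≥1 is pooled and the size of the change is not shown.

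Two programmers could produce different tables from the same sentence, and neither table shows graded change.

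**3. Share of transition types hidden under Reading A (illustration only).** The number of grades is not given, so let the scale run from 0 to k (assumption).

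- Ordered pairs of different grades: k(k+1).
- Pairs with both grades ≥1: k(k−1).
- Share hidden: (k−1)/(k+1).

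| Assumed scale | Hidden / all changes | Share | Hidden / all decreases |
|---|---|---|---|
| 0–2 | 2 / 6 | 33% | 1 / 3 |
| 0–3 | 6 / 12 | 50% | 3 / 6 |
| 0–4 | 12 / 20 | 60% | 6 / 10 |
| 0–5 | 20 / 30 | 67% | 10 / 15 |

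These are types of transition, each given equal weight. They are not expected numbers of patients or events.

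**4. Whether general summaries fill the gap.** The general principles (Part C 5.1, later-onset 4.4) promise percentages in each category. Suppose one participant goes from grade 2 to 1 and another from 1 to 2. The percentages at both times are identical, although two participants changed. A distribution by visit is not a within-subject shift.

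**The case against.** The strongest case against has four parts.

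- **The text does not state that grade changes within ≥1 count as maintained.** It uses 0 and ≥1 to define predose strata and is silent on postdose grades. This stands. A reader might infer an explicit rule that discards every such change, and the SAP contains none.
- **Reflexes have other routes into the report.** Both SAPs promise descriptive summaries for endpoints. Later-onset Part B plans figures. In Part C, worsening or new "findings noted from the physical or neurological examinations will be reported as AEs as" appropriate, and adverse events are tabulated within 24 and 72 hours of dosing. This stands in part, so it would be wrong to say that the 0 versus ≥1 table is the only analysis. But the summaries are marginal, the figures are undefined, and adverse event reporting depends on investigator judgement and is listed as a separate endpoint. The later-onset SAP does not contain the adverse event statement.
- **The infantile-onset SAP is an imperfect precedent.** It uses Sections 1 and 3 of the Hammersmith infant examination, a different instrument, and it shares the 0 versus ≥1 display. This stands as a caution. The precedent is for the format of the shift table, which carries over to any ordinal item.
- **Shift tables will be sparse.** Later-onset Part B has 8 and 16 participants, with seven dosing or sham days. This also stands. It is a reason to keep the tables compact, but not to omit the grades.

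None of this supplies the missing chronic reflex comparison in Part C. At most, the general summary rule could be stretched to cover it, without naming a display.

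**Conclusion.** The point holds as a loss of sensitivity and an undefined rule. In Part C and later-onset Part B the reflex-specific tables reduce an ordinal grade to two predose categories and leave the postdose classification open. On the natural reading they cannot show weakened or heightened reflexes that remain present. Part C also specifies no chronic reflex comparison for a primary endpoint. That gap rests on no assumption and looks inadvertent, since the later-onset SAP has such a section.

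A reader might go further and conclude that a neurological signal will be missed, or attach a probability to missing one. The documents do not support that. They give no number of grades and no rate of grade change, and partial routes exist. The 40 Part C participants are an upper bound for this table, because 5.7.3.2 covers only those aged 2 years or older. The 33% to 67% range is an illustration that rests on the assumed scale and on Reading A. The change is still worth making: it is specific and cheap, and it concerns a named safety endpoint.

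**What to change.** 1. In Part C 5.7.3.2 and later-onset 6.1.3, state how postdose and later predose grades are classed, and define gained, lost and maintained from that.
2. In both sections, add for each reflex a shift table on the recorded grade: from predose to the lowest and to the highest postdose grade on each dosing day; and from Day 1 predose to the lowest and to the highest grade among later predose values and Day 302. This follows the infantile-onset SAP and supplies the chronic reflex display that Part C lacks.
3. Keep the 0 versus ≥1 table as a secondary display.

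The cost is SAP wording and a few more tables, covering three dosing days in Part C and seven dosing or sham days in later-onset Part B. Many cells will be sparse. No new data are needed.
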